3.5 Determination of sample size

Sample size was calculated based on available data from peer-review publications complemented with reasonable estimates of efficacy for those experimental groups that have not been previously tested. For these calculations, the efficacy of the control arm (Albendazole 400mg in a single dose), was obtained for *T. trichiura* and hookworms from a systematic review and meta-analysis where

temporary trends in efficacy (with the corresponding confidence intervals) were incorporated (Table 3)[4]. For the efficacy of the control arm against *S. stercoralis*, an alternative source was used [5], since the systematic review by *Moser et al* did not include this species; for that reason, a clinical trial that included an arm of Albendazole 400mg for 3 consecutive days was used, assuming a "best case scenario" for the efficacy of the control group; this estimated efficacy is also in the range of a systematic review assessing the efficacy of Albendazole at various (but not single) doses[5]. For the FDC at single dose, the calculations were based on the estimated efficacies (and their corresponding confidence intervals) in a systematic review that calculated the Relative Risks of cure of diverse drug regimens against Albendazole 400mg single dose (Table 3)[6,7]. For. *S. stercoralis*, the estimated efficacy of FDC was calculated based on a recent clinical trial using lvermectin single and multiple-dose regimens [8]. Finally, for the FDC in 3-dose regimens, considering its use in public health, deployment logistics in MDA campaigns and expected impact of the FDC, we estimated that an improvement of at least 15 percentage points would be the minimum improvement in efficacy to be demonstrated in order to make the FDCx3 regimen worth considering.

Sample size was calculated estimating the efficacy of the different experimental drug or combinations for each of the STH of interest [9,10], and gathering the individual samples sizes for the study. The sample size was calculated for pairwise comparisons of the expected Cure Rates for three study groups with an overall significance level of 5% adjusted for multiple tests by Bonferroni's correction, 80% power and inflated for 10% lost-to-follow-up.

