The estimated total number of participants for the adaptive design is 1223 (*T. trichiura* 625, *S. stercoralis* 286 and hookworm 312). This sample size is powered to be able to measure efficacy for all three species in the phase III component. The sample size for the phase II component is 20% of the total participants for *T. trichiura* (126 participants). The remaining 80% of the *T. trichiura* participants will be randomised in the phase III component. Table 4 details the stratification of the participants per species with a 10% lost-to-follow-up.

The total number of participants to be included in this clinical trial is 1223 (126 in phase II and 1097 in phase III). Following randomisation, 251 participants will be allocated to the ALB treatment arm, 427 will be allocated to the FDC treatment arm and 419 in the FDCx3 treatment arm. Table 4 details the stratification of the participants per species with a 10% lost-to-follow-up.

The 10% lost-to-follow-up inflated sample sizes of the ALB-group for *T. trichiura, S. stercoralis* and hookworm are 129, 47 and 101 respectively, and the corresponding sample sizes of the individual experimental treatment groups are 248, 120, and 101 for FDC-group and 248, 119 and 110 for FDCx3-group. The corresponding powers of each of the tests are 91%, 100% and 80% to compare the CRs of *T. trichiura* in ALB vs FDC, ALB vs FDCx3 and FDC vs FDCx3 respectively; 95%, 100% and 80% to compare the CRs of hookworm respectively for ALB vs FDCx3 and FDC vs FDCx3 comparisons. We do not compare CRs of hookworm in ALB and FDC as they are known to be the same. These powers were computed assuming that the expected CRs for *T. trichiura* are 23.7%, 43.7% and 59% in the ALB, FDC and FDCx3 groups respectively; 45%, 79% and 94% for *S. stercoralis* and 79.5%, 79.5% and 95% for hookworm. **Table 3** and **Table 4** show the sample size calculation according to the expected Cure Rate for each drug and helminth of interest, and the resulting sample size inflated by 10% due to the estimated lost-to-follow-up. Assumptions used for the sample size calculations (e.g. expected CRs, lost-to-follow-up, etc) should be checked during the interim analysis.

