5.3 Efficacy analysis

5.3.1 Hypothesis

The main hypothesis is that FDC (either at single or 3-day regimens) will be more effective against STH than the current strategy (single dose ALB alone).

Specific hypotheses:

- Primary Efficacy Endpoint: Higher estimated CR for *T. trichiura* 21 days after treatment, using microscopy in participants allocated to arms 2 and 3 than to arm 1.
- Secondary Efficacy Endpoint(s):
 - Higher estimated CR for hookworm and *S. stercoralis* 21 days after treatment using microscopy in participants allocated to arms 2 and 3 than to arm 1.
 - Higher estimated ERR for *T. trichiura* 21 days after treatment using microscopy in participants allocated to arms 2 and 3 than to arm 1.
 - Higher estimated CR for hookworm, *T. trichiura* and *S. stercoralis* 21 days after treatment, using qPCR in participants allocated to arms 2 and 3 than to arm 1.

5.4 **Primary efficacy outcomes analysis**

The primary efficacy endpoint for the efficacy phase III trial is the cure rates for *T. trichiura* 21 days after treatment using microscopy. The analysis will be conducted on the ITT population and in the sensitivity population (per protocol). The analysis will include both Phase II and Phase III participants. The Cochran–Mantel–Haenszel (CMH) test, controlling the effect of site if that is appropriate (sufficient participants), will be used to compare the cure rates for the 3 treatment groups. A participant is considered cured if the baseline egg count or larval count is not 0, and the post-treatment egg count or larval count is 0. Similarly, a participant is considered to have treatment failure if the baseline egg or larval count is not 0.

A total of 2 stool samples (1 pre-treatment and 1 post-treatment) will be obtained from each participant. The primary efficacy analysis will be based on ITT population. Efficacy for each type of infection will be analysed separately. A participant with multiple infections will be included in the analysis of each target species that the participant is infected with.

Stool sample collected pre-treatment will be used for the baseline information, and stool sample collected post-treatment will be used for the post-treatment information in the statistical analysis.

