5.4.1 Secondary efficacy outcomes analysis

The analysis will be conducted on the ITT population and in the sensitivity population (per protocol)

The secondary efficacy endpoints for the phase II and phase III are the following:

- CR for *T. trichiura* 21 days after treatment, as determined by microscopy (phase II).
- CR for hookworm and *S. stercoralis* 21 days after treatment, as determined by microscopy (phase II and phase III).
- ERR for *T. trichiura* 21 days after treatment, by microscopy (phase II and phase III).
- ERR for hookworm 21 days after treatment, by microscopy (phase II and phase III).
- CR for *T. trichiura*, hookworm and *S. stercoralis*, by PCR (phase II and phase III).
- Parasite burden decrease after 21 days for *T. trichiura*, hookworm, and *S. stercoralis*, by PCR (phase and phase III).

The first 2 endpoints above regarding the CR will be analyzed using the same approach as the primary endpoint analysis.

Egg reduction rate (ERR) for each species (for *T. trichiura* and hookworms) at end of treatment period will be estimated. *S. stercoralis* will not be evaluated by this analysis.

$$ERR (geometric mean) = 1 - \frac{e^{\frac{1}{n}\sum\log(EPG \ follow \ up+1)} - 1}{e^{\frac{1}{n}\sum\log(EPG \ baseline+1)} - 1}$$

The logarithmic transformation will be conducted. As there may be participants with a count of zero eggs in the post-treatment stool sample, a value of 1 will be added to total egg count at baseline and total egg count at post-treatment so that the logarithmic transformation can be applied. The geometric mean will be used to summarize the mean egg count at pre-treatment and post-treatment visits and in the calculation of the mean percent egg reduction. Treatment differences will be evaluated by an analysis of covariance (ANCOVA), in which the logarithm of the egg count at post-treatment is the dependent variable, site (if appropriate), and treatment as fixed effect, and the logarithm of the egg count at pre-treatment is the covariate. Baseline egg count will also be analysed as an independent variable that conditions treatment response [11].

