5.4.3 Sub-group analyses

Subgroup analyses will be performed for the primary efficacy outcome on the ITT population. The variables for the subgroup analysis will include:

- Ivermectin drug exposure: categorized by >400 μg/Kg vs ≤400 μg/Kg
- Age: categorized by school-age children (5 to 14 years-old) & young adults (15 to 18 years-old).
- Co-infection: categorized by mono-infected vs co-infected
- Infected with HIV vs no infected with HIV
- Worm burden: categorized by WHO categories of egg burden categories measured by Eggs Per Gram (EPG) through Kato-Katz method [14]:

Species	Light	Moderate	Heavy	
T. trichiura	1 – 999	1000 – 9999	≥10000	
Hookworms	1 – 1999	2000 – 3999	≥4000	
A. lumbricoides	1 - 4999	5000 - 49999	≥50000	

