5.4.4 Multiplicity

Multiplicity adjustment will not apply to the primary and secondary outcome analyses.

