5.7 Interim analyses

Two interim analyses are planned: 1) after the end of the phase II component for decision making to move to the phase III component; 2) after 50% of the study participants are enrolled. Regular evaluation of the safety data every 3 months will be performed by the DSMB. The study is designed as a superiority trial, so all tests will be two-sided and an overall significance level will be 0.05 In the interim efficacy analysis, the expense function alpha with the O'Brien-Fleming approach will be used to determine the type I error rate for each interim and final analysis.

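### The primary T. trichiura cure-rate test leaves out baseline egg count, which the SAP already treats as related to response; this costs some efficiency, mainly for FDC vs FDCx3, and causes no bias

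*SAP*

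**What the plan says.** **Primary test.** SAP 5.4 and Protocol 9.5.2 compare T. trichiura cure rates across the three arms with a CMH test, described as "controlling the effect of site if that is appropriate (sufficient participants), will be used to compare the cure rates for the 3 treatment groups". Site is the only adjustment factor named, and it is conditional.

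**Baseline count elsewhere in the SAP.** One pre-treatment stool sample is taken from each participant, and a positive baseline result puts the child in the analysis set. In SAP 5.4.1 the log baseline count is the covariate in the ERR analysis of covariance, and the section adds: "Baseline egg count will also be analysed as an independent variable that conditions treatment response". SAP 5.4.3 lists a subgroup factor for the primary outcome: "Worm burden: categorized by WHO categories of egg burden categories".

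**General covariate sentence.** SAP 5.4.1 also says that relevant covariates will be included. It sits in the secondary-outcome section, and HIV in Mozambique is the only covariate it names.

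**Randomisation.** Under SAP 3.4, phase III is stratified by species. Phase II uses simple randomisation to 26, 50 and 50 children within a weight-group enrolment scheme. Neither part balances arms on infection intensity, and both enter the primary analysis.

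**The concern.** The plan treats baseline egg count as related to response in the ERR model and in the subgroup list, but does not use it in the primary test. A subgroup table shows whether the effect differs by intensity. It does not adjust the overall comparison.

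If heavier infections are harder to clear, part of the spread in cure is explained before treatment starts. Leaving that part in the residual gives a less powerful test and leaves any chance imbalance in intensity uncorrected. The contrast most exposed is FDC vs FDCx3. It is planned at exactly 80% power, it drives the size of the two FDC arms, and it addresses the 15-point improvement that SAP 3.5 sets as the minimum for the three-day regimen to be worth considering.

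**Working it through.** **Inputs from the documents**
- Expected T. trichiura cure rates "are 23.7%, 43.7% and 59% in the ALB, FDC and FDCx3 groups respectively" (SAP 3.5).
- Evaluable children 116, 223 and 223; stated powers 91%, 100% and 80% (SAP Table 3).
- Sizing at an "overall significance level of 5% adjusted for multiple tests by Bonferroni's correction, 80% power and inflated for 10% lost-to-follow-up"; three pairwise tests give 0.05/3 = 0.0167.
- Two-sided tests: "The study is designed as a superiority trial, so all tests will be two-sided" (SAP 5.7).
- Analysis alpha: "Multiplicity adjustment will not apply to the primary and secondary outcome analyses" (SAP 5.4.4), so results are also given at 0.05.
- Missing outcomes count as failures (SAP 4.1 and 5.1.5).

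**Input not in the documents.** R², the share of cure/no-cure variance explained by baseline count, is assumed and shown as a range.

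**Step 1: reproduce the plan's figures.** For two equal arms, power = Φ{[(p2 − p1) − z·s0]/s1}, with s0 = √[2p̄(1 − p̄)/n] and s1 = √{[p1(1 − p1) + p2(1 − p2)]/n}.

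For FDC vs FDCx3: p1 = 0.437, p2 = 0.59, p̄ = 0.5135, n = 223, z = 2.394, s0 = 0.0473, s1 = 0.0468. Then (0.153 − 2.394 × 0.0473)/0.0468 ≈ 0.848, and Φ(0.848) = 80.2% (stated 80%). The same method with unequal arms gives 90.6% for ALB vs FDC (stated 91%) and 100% for ALB vs FDCx3 (stated 100%). The dropout inflation also reproduces: 116/0.9 gives 129 and 223/0.9 gives 248.

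**Step 2: effect of adjustment on FDC vs FDCx3.** Adjustment acts like multiplying n by 1/(1 − R²). The last column is 223 × (1 − R²), rounded up.

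| Assumed R² | Approx. odds ratio for cure per SD of log count | Effective n per arm | Power, alpha 0.0167 | Power, alpha 0.05 | n per arm for 80% at 0.0167 |
|---|---|---|---|---|---|
| 0 | 1 | 223 | 80.2% | 90.1% | 223 |
| 2% | 0.74 | 227.6 | 81.1% | 90.7% | 219 |
| 5% | 0.61 | 234.7 | 82.5% | 91.5% | 212 |
| 10% | 0.50 | 247.8 | 84.7% | 92.9% | 201 |
| 20% | about 0.3 | 278.8 | 89.1% | 95.3% | 179 |

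**Step 3: check by simulation**, holding the marginal cure rates at the plan's values.
- At 0.0167, with odds ratios of 0.74, 0.61, 0.50 and 0.37, the plain CMH has 79–80% power and the adjusted logistic test 81%, 83%, 85% and 87%. At 0.3 the adjusted test reaches about 90%.
- At 0.05, the gains for odds ratios of 0.74, 0.6, 0.5 and 0.3 are about 1, 1, 2 and 5 points.
- CMH stratified by count quartile gives 80%, 83%, 84% and 87% at 0.0167 for the same four odds ratios as in the first line. Three WHO-type classes give 81%, 82%, 83% and 85%, with an assumed split of 70/28/2%.

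**Step 4: the contrasts in the primary hypothesis.** At 0.0167, ALB vs FDC goes from 90.6% to 91.2%, 92.1%, 93.6% and 96.2% for R² of 2%, 5%, 10% and 20%. ALB vs FDCx3 stays at 100%. At 0.05 they start at 96% and 100%.

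**Step 5: features that shrink the gain.**
- Missing = failure: with 10% missing per arm, the cure rates become 0.9 × 43.7% = 39.3% and 0.9 × 59% = 53.1%. With 248 per arm, unadjusted power is 75.4% at 0.0167. The gain is about 2, 4 and 8.5 points for odds ratios of 0.6, 0.5 and 0.3.
- Site: if 30% of log-count variance lies between two sites (an assumption), the gain over a site-stratified CMH at an odds ratio of 0.5 is about 3 points instead of 5.

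**Step 6: validity.** Under the null, the plain CMH rejected in 0.0159 of 200,000 simulated trials, against a nominal 0.0167. In a smaller check of 8,000 trials, the plain, stratified and adjusted tests all lay between 0.0122 and 0.0127. There was no sign of inflation.

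**The case against.** **The primary hypothesis hardly benefits.** It compares arms 2 and 3 with arm 1, and those contrasts have 91% and 100% planned power. This stands. A reader might infer that the omission endangers the trial's main conclusion; the plan's own power figures do not support that.

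**The alpha of 0.0167 belongs to the sizing.** SAP 5.4.4 drops the multiplicity adjustment, and at 0.05 FDC vs FDCx3 already has 90% power. This also stands, which is why both alphas are shown. The disagreement between SAP 3.5 and 5.4.4 is a separate matter.

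**The prognostic effect is unknown.** The SAP's statement cites a paper of which only the title is visible here, and that title concerns single-dose albendazole, the control regimen. No effect size can be taken from it. If the count does not predict cure, the gain is zero. The size below is therefore conditional.

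**The plan does not ignore egg burden.** It is a planned subgroup factor for the primary outcome and an ERR covariate. That is correct. The gap is confined to the primary test, and neither the subgroup list nor the general covariate sentence closes it.

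**CMH is a sound test.** It is valid under randomisation. A reader might infer bias from the missing covariate, but nothing in the documents supports that. Validity does not answer the efficiency point, however, because the adjusted analysis is also valid and uses data already in hand.

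**Conclusion.** The point holds as one of efficiency. The primary test adjusts for site at most and leaves out a baseline value that is collected on every child and that the SAP itself says conditions response.

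For FDC vs FDCx3 the gain is about 1 to 9 points at 0.0167 (80% to 81–89%) and about 1 to 5 points at 0.05 (90% to 91–95%). It is somewhat smaller with missing = failure or where site already captures intensity. These figures rest on assumed R² values of 2% to 20%, the plan's cure rates and 223 evaluable children per arm. For the contrasts with ALB the gain is small or nil unless the count is strongly prognostic.

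The change is worth making because it is nearly free and because FDC vs FDCx3 has no margin at the sizing alpha. The trial does not depend on it.

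**What to change.** Before unblinding, define the primary analysis in SAP 5.4 as a logistic model for T. trichiura cure with arm, site and log baseline eggs per gram. Report each contrast as a standardised (marginal) cure-rate difference with its confidence interval, so that the quantity estimated is still a cure-rate difference; an adjusted odds ratio alone would answer a different question. Keep the site-stratified CMH as a sensitivity analysis.

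A simpler option is to add egg-count class as a CMH stratum alongside site. In simulation at 0.0167, quartiles came close to the model, while three WHO-type classes gained less (81–85%, on the assumed split).

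Cost: no new data. The logistic route needs a standardisation step. Protocol 9.5.2 names the CMH test too, so its wording must be changed to match, with whatever approval that requires under Protocol 10.1. The stratified route may give sparse site-by-class cells, so a rule for collapsing classes should be fixed in advance.

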5.4.1 Secondary efficacy outcomes analysis

The analysis will be conducted on the ITT population and in the sensitivity population (per protocol)

The secondary efficacy endpoints for the phase II and phase III are the following:

- CR for *T. trichiura* 21 days after treatment, as determined by microscopy (phase II).
- CR for hookworm and *S. stercoralis* 21 days after treatment, as determined by microscopy (phase II and phase III).
- ERR for *T. trichiura* 21 days after treatment, by microscopy (phase II and phase III).
- ERR for hookworm 21 days after treatment, by microscopy (phase II and phase III).
- CR for *T. trichiura*, hookworm and *S. stercoralis*, by PCR (phase II and phase III).
- Parasite burden decrease after 21 days for *T. trichiura*, hookworm, and *S. stercoralis*, by PCR (phase and phase III).

The first 2 endpoints above regarding the CR will be analyzed using the same approach as the primary endpoint analysis.

Egg reduction rate (ERR) for each species (for *T. trichiura* and hookworms) at end of treatment period will be estimated. *S. stercoralis* will not be evaluated by this analysis.

$$ERR (geometric mean) = 1 - \frac{e^{\frac{1}{n}\sum\log(EPG \ follow \ up+1)} - 1}{e^{\frac{1}{n}\sum\log(EPG \ baseline+1)} - 1}$$

The logarithmic transformation will be conducted. As there may be participants with a count of zero eggs in the post-treatment stool sample, a value of 1 will be added to total egg count at baseline and total egg count at post-treatment so that the logarithmic transformation can be applied. The geometric mean will be used to summarize the mean egg count at pre-treatment and post-treatment visits and in the calculation of the mean percent egg reduction. Treatment differences will be evaluated by an analysis of covariance (ANCOVA), in which the logarithm of the egg count at post-treatment is the dependent variable, site (if appropriate), and treatment as fixed effect, and the logarithm of the egg count at pre-treatment is the covariate. Baseline egg count will also be analysed as an independent variable that conditions treatment response [11].

Cure rates will be also calculated by qPCR. For this, a participant is considered cured if the mean Ctvalues are less or equal than 40 at baseline, and greater than 40 after treatment. When there are nondetectable levels of DNA in the sample, it will be categorized with a Ct-value equal to 50. Cochran– Mantel–Haenszel (CMH) test, controlling the effect of site if that is appropriate (sufficient participants), will be used to compare the cure rates for the 3 treatment groups. In addition, Kappa test and the Fisher 's exact test or chi - square test will be used to compare the CR obtained by Kato-Kats and PCR for the same treatment arm.

Correlation between Kato-Katz counts and qPCR Ct-values will be explored through Pearson's or Spearman's (according to the underlying distribution) correlation tests. Different regression methods to predict EPGs based on Ct-values will be explored.

Increases in Ct-values after treatment will be considered as a reduction in parasite load. To measure whether the increase in ct is significant in each treatment arm, the "Wilcoxon signed-rank test" will be used.

The qPCR will allow the identification of hookworm species (*N. americanus* and *A. duodenale*), so it will be evaluated if there are differences in the response to treatment for these species. Kappa test will be used for the evaluation of both tests in the calculation of CR.

Relevant covariates will also be included in the data analysis. Particularly, HIV infection will be assessed as a covariate in participants recruited in Mozambique.

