2.1.2.2 Secondary objectives

- 1. To evaluate the **efficacy** of the FDC as a single dose or 3-day single dose regimen for the treatment of hookworm and *S. stercoralis*.
- 2. To evaluate the safety of the FDC as a single dose or 3-day dose regimen for the treatment of *T. trichiura*, hookworm and *S. stercoralis*.
- 3. To evaluate the performance of PCR in calculating the primary outcome measurement (efficacy) compared to an egg counting method (Kato-Katz).
- 4. To evaluate the frequency of known ALB resistant alleles in hookworm and *T. trichiura* in the three treatment arms before and after treatment.

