2.2 Outcomes

2.2.1 Primary outcome

Safety evaluations: Safety evaluations and measurements, including adverse events (AEs), vital signs, physical examination, weight, height and BMI will be assessed from the time of signing the informed consent through to post-treatment follow-up visit. To evaluate safety, participants will be evaluated as detailed in the schedule of visits (Table 1 and Table 2). All AEs during all study visits, will be noted in the CRF for each participant. A close surveillance, 3 hours post-treatment, will be conducted each day a participant receives treatment.

Any clinically significant abnormalities persisting at the end of the study will be followed up by the study physician until resolution or until a clinically stable endpoint is reached.

A Data Safety Monitoring Board (DSMB) will monitor the ongoing safety of the participants during the study.

Efficacy evaluation: Anti-helminthic primary efficacy, measured by cure rate will be determined by analysing a stool sample taken 21(+/-7) days after completing treatment with Kato Katz, Baermann. [1,2]

Cure is defined as absence of the species of STH in participants who had a positive egg count and/or larva for that STH species at baseline. Cure rate (CR) is defined as the proportion of individuals cured (absence of any egg and/or larva) to the total of those infected at baseline with each particular species of STH.

Table 1. Schedule of Activities Phase II Component (KENYA only)

	1							r	
Procedures	Study Visit 0 Screening Day -7 to -1	Study Visit 1 Enrolment/ Baseline Day 0	Study Visit 2 Day 1	Study Visit 3 Day 2	Study Visit 4 Day 3	Study Visit 5 Day 7	Study Visit 6 Day 21+/-7 day post treatment	Unscheduled	Withdrawal
Informed consent ¹	Х								
Informed assent ²	Х								
Stool collection kit delivered	Х						Х		
Stool collection ³	Х						Х		Х
Stool analysis (Baermann and Kato-Katz) ⁴	х						Х		х
Inclusion and Exclusion criteria	Х	Х							
Demographics ⁵	Х								
Physical exam ⁶	Х	Х					Х	Х	Х
Vital signs ⁷	Х	Х	Х	Х	Х	Х	Х	Х	Х
Height	Х	Х							
Weight	Х	Х							
Urine Pregnancy test ⁸	Х								
Haematuria strip test as proxy for Schistosoma h	х								
Randomization and treatment assignation		х							
Study drug administration		X ⁹	X ¹⁰	¹¹ X					
Acceptability questionnaire Arm 1 (ALB)									
Acceptability questionnaire Arm 2 (FDCx1)		х							
Acceptability questionnaire Arm (FDCx3)				х					
PK blood sampling		X ¹²	XI	XI					
Study drug accountability		Х	Х	Х			Х		Х

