²⁵ Treatment Day 2. Only for participants in treatment Arm 3. Close observation for 3 hours post-treatment for safety evaluations.

²⁶ Adverse events will be assessed by direct observations of the study physician, or reported by the participant or parent/guardian.

rate will be determined by analysing a stool sample taken 21(+/-7) days after completing treatment with qPCR.

At pre- and post-treatment visits a duplicate Kato-Katz test will be performed on a fresh stool sample collected <24 hours before examination. Baermann method will also be performed in parallel to Kato-Katz for the search of *S. stercoralis*. Evaluation by qPCR will be performed in pre- and post-treatment samples.

Pharmacokinetic outcome measures (only phase II): Two blood samples for population PK analysis will be collected for every participant by finger prick using the mitra devices [3] in the phase II component to adjust a population pharmacokinetic model. Additionally, a NCA will be performed to obtain (Cmax), time to reach Cmax (Tmax) and area under the curve (AUC) of ALB and IVM. A complete description of the pk analysis can be found in the statistical analysis plan for pharmacokinetics.

Participant acceptability/palatability outcome measures (only phase II):

Facial hedonic scale and implied numerical rating scale (NRS) will be included in the Phase II component of the trial to measure attributes for the FDC orodispersible formulation in terms of taste, aftertaste; mouth feel; smell; time needed to dissolve/disperse (duration of administration). Secondary aspects will include visual aspects: embossing, surface aspects and colour. Refer to the protocol Section 9.5.2 for details.

Resistance: Whole genome sequencing, next-generation DNA sequencing and omic approaches will be used to assess underlying factors associated with low treatment response including assessment and evaluation of new protocols for sample processing and sequencing.

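### The Kato-Katz and PCR cure rates come from the same children, but SAP 5.4.1 compares them with Fisher's exact or chi-square, neither of which tests a paired difference

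*SAP*

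**What the plan says.** Phase III secondary objective 3 in SAP 2.1.2.2 is "To evaluate the performance of PCR in calculating the primary outcome measurement (efficacy) compared to an egg counting method (Kato-Katz"). The protocol synopsis adds the Baermann technique to this objective; the objectives table in protocol section 3 names Kato-Katz only.

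Two statements fix the data structure. SAP 5.4: "A total of 2 stool samples (1 pre-treatment and 1 post-treatment) will be obtained from each participant". SAP 2.2.2: "Evaluation by qPCR will be performed in pre- and post-treatment samples". The footnotes to the SAP schedules of activities add that PCR uses an aliquot of the collected stool.

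For the method comparison, SAP 5.4.1 plans:
- kappa together with Fisher's exact or chi-square: "test will be used to compare the CR obtained by Kato-Kats and PCR for the same treatment arm";
- kappa a second time: "Kappa test will be used for the evaluation of both tests in the calculation of CR";
- Pearson or Spearman correlation of Kato-Katz counts with Ct, and exploratory regression of eggs per gram on Ct.

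A Wilcoxon signed-rank test is planned for Ct before and after treatment: "To measure whether the increase in ct is significant in each treatment arm". Protocol 9.5.3 plans only correlation and kappa for the method comparison. Neither document names McNemar's test or an interval for a paired difference in proportions.

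Cure is defined differently by method. SAP 2.2.1 relates microscopy cures "to the total of those infected at baseline with each particular species of STH", with infection shown by a positive egg or larva count. SAP 5.4.1 calls a child cured by PCR if the mean Ct is 40 or less at baseline and above 40 after treatment.

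**The concern.** Within an arm, every child contributes one microscopy result and one PCR result. Fisher's exact test and the usual chi-square for two proportions assume separate children in the two groups. The sentence in SAP 5.4.1 can be carried out in two ways, and both fail:

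- **Two independent groups.** The variance omits the within-child covariance. When the methods agree beyond chance, the standard error is too large and the test rejects too rarely.
- **The Kato-Katz by PCR cross-table.** The test then asks whether the two results are associated. It can be overwhelmingly significant when the cure rates are identical.

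Kappa does use the pairing, but it measures agreement: two methods can have the same kappa with or without a systematic difference in cure rate. The correlation and the signed-rank test address other questions. Objective 3 asks how PCR performs in calculating efficacy, so whether it gives a different cure rate is central to it.

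The SAP also leaves open which children enter the comparison. Microscopy cure is tied to a positive baseline count and PCR cure to a baseline Ct of 40 or less; the PCR denominator is never stated.

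**Working it through.** The documents give no power or error rate for this comparison, so there is no figure of theirs to reproduce.

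**Inputs from SAP Table 3.** Evaluable n and expected microscopy cure rate (CR): T. trichiura FDC 223, 43.7%; T. trichiura ALB 116, 23.7%; hookworm ALB 91, 79.5%. Two-sided alpha is 0.05 (SAP 5.7).

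**Assumed, because the documents give no values.** PCR cure rate 5, 7.7 or 10 points below microscopy; kappa 0.2, 0.4 or 0.6.

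**Cell probabilities.** With cure rates p1 (microscopy) and p2 (PCR), chance agreement is Pe = p1·p2 + (1−p1)(1−p2). Total discordance is d = (1−kappa)(1−Pe). The discordant cells are b = (d + p1 − p2)/2 (cured by microscopy only) and c = (d − p1 + p2)/2 (cured by PCR only).

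FDC arm, p1 = 0.437, p2 = 0.360, kappa 0.6:
- Pe = 0.1573 + 0.3603 = 0.5176
- d = 0.4 × 0.4824 = 0.1929
- b = 13.5%, c = 5.8%

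**Standard errors of the difference.**
- Unpaired: √{[p1(1−p1) + p2(1−p2)]/n} = √(0.4764/223) = 4.62 points.
- Paired: √{[d − (p1−p2)²]/n}. At kappa 0.6 this is √(0.1870/223) = 2.90 points; at kappa 0.4 it is 3.57 and at kappa 0.2 it is 4.13.

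**Power, by simulation** (200,000 multinomial draws per scenario; asymptotic McNemar; kappa 0.2 / 0.4 / 0.6):

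| Arm | Gap (points) | Unpaired chi-square | McNemar |
|---|---|---|---|
| T. trichiura FDC | 5 | 16 / 12 / 8% | 22 / 28 / 40% |
| T. trichiura FDC | 7.7 | 36 / 35 / 31% | 46 / 58 / 76% |
| T. trichiura FDC | 10 | 59 / 60 / 63% | 68 / 81 / 94% |
| T. trichiura ALB | 7.7 | 29 / 26 / 22% | 38 / 49 / 66% |
| Hookworm ALB | 7.7 | 20 / 16 / 12% | 28 / 36 / 48% |

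Exact McNemar in the FDC arm at 7.7 points gives 41.5 / 53.1 / 71.3%.

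**Type I error with both cure rates at 43.7%, n = 223.** Unpaired chi-square rejects 2.9 / 1.2 / 0.2% of the time against a nominal 5%. Asymptotic McNemar rejects 5.0%, exact McNemar 3.9 / 3.8 / 3.6%.

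**Cross-table reading with identical cure rates.** With equal margins phi equals kappa, and the expected chi-square is about n × phi²: 223 × 0.04 = 8.9, 223 × 0.16 = 35.7, 223 × 0.36 = 80.3. The 5% critical value is 3.84, so the test would usually be significant with no difference in cure rate to find.

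**Hypothetical counts, FDC arm.** Both cured 75, microscopy only 22, PCR only 4, neither 122. Microscopy CR is 97/223 = 43.5%, PCR CR is 79/223 = 35.4%, kappa 0.76. As independent groups: chi-square p = 0.081, Fisher p = 0.099. Paired: exact McNemar p = 0.0005. Cross-table chi-square: p about 2 × 10⁻³⁰, which reflects association only.

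**The case against.** The strongest reply concerns importance. None of the hypotheses in SAP 5.3.1 is about a difference between methods; all compare arms. Kappa appears twice, with correlation and regression beside it, so Fisher or chi-square is an addition to an agreement analysis. Both cure rates will be reported whatever test is used, and no trial decision rests on this p-value. All of this stands and limits the consequence, but it does not make the planned test suitable.

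The size also depends on assumptions. At a 15-point gap in the FDC arm, power is 94 / 96 / 99% unpaired and 96 / 99 / 100% with McNemar, so the loss almost disappears there; in hookworm ALB it remains (64 / 66 / 69% against 73 / 86 / 99%). At kappa 0.2 the exact McNemar test gains little, and in hookworm ALB at 7.7 points nothing (about 20% for both). The power figures use the full evaluable numbers; a set restricted to children positive by both methods would be smaller.

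On denominators, SAP 5.4.1 defines when a child is cured by PCR, not who is counted. One could keep the microscopy-positive children for both methods. The firm statement is therefore that the PCR denominator is unspecified. On Baermann, the SAP wording matches its own objective and the protocol's objectives table; the discrepancy is with the synopsis.

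**Conclusion.** The concern holds. The planned test is wrong for paired data under either reading, and nothing else in the plan tests the difference in cure rates. Under the independent-groups reading the cost is lost power: small when agreement is low or the gap is large, substantial when agreement is good and the gap moderate (31% against 76% in the FDC arm at 7.7 points and kappa 0.6). It does not inflate type I error. Under the cross-table reading the p-value answers a different question. These sizes rest on the assumed PCR cure rates and kappas; the mismatch between test and design does not.

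The effect is confined to secondary objective 3. The primary endpoint, the sample size and the between-arm CMH comparison of PCR cure are untouched. The change should be made, since it is cheap and the objective is stated.

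A lesser matter: the within-arm signed-rank test on Ct is valid for showing a decrease. However, S. stercoralis "will not be evaluated by this analysis" for egg reduction, so no between-arm comparison of its infection intensity is planned.

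**What to change.** In SAP 5.4.1:

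1. Replace Fisher's exact or chi-square with McNemar's test (exact when discordant pairs are few), and report the paired difference in cure rate with a 95% CI, per arm and species. Keep kappa for agreement.
2. State the paired set. Children positive by both methods at baseline is a workable choice. It drops microscopy-positive, PCR-negative children, and also PCR-positive children who are microscopy-negative for that species, so both cure rates will differ from those in the main analyses. Report how many are dropped on each side.
3. Say how children without a post-treatment result enter the pairs, given that SAP 5.1.5 counts missing efficacy data as failure.
4. Name Baermann as the microscopy method for S. stercoralis, and align the synopsis, the protocol objectives table and the SAP.

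Optional: compare post-treatment Ct between arms with a rank-based analysis adjusted for baseline Ct and site, ranking undetectable (Ct 50) as the lowest burden, and keep the signed-rank test as descriptive.

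The cost is SAP wording only, with the same data and software.
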